1.4 Convalescent Plasma Information

Convalescent Plasma may be collected by either apheresis (often in combination with concurrent platelet apheresis collection) or via traditional phlebotomy followed by centrifuge

separation. For purposes of being able to safely expedite and optimize plasma donation for an otherwise healthy donor apheresis is the preferred procedure.

Donors must undergo screening as per guidelines set out by the FDA for collection of COVID-19 Convalescent Plasma.

We have previously initiated an IRB approved Convalescent Plasma Donor Program and are actively recruiting donors. Donors are being recruited in collaboration with the Georgia Department of Public Health, hospital epidemiology program and through public outreach. Donors are having sample(s) of their sera stored. Currently, quantitation of IgG Ab titers against COVID-19 is not available. Once testing is approved and commercially available potential donors will have their IgG Ab titers measured.

1.5 Risks and Benefits of Convalescent Plasma Therapy

It is anticipated that the risks associated with the infusion of convalescent donor plasma will be low, and of those events, most are expected to be of low grade (Grade 2 or less) severity. **xxviii,xxxviii,xxxii** The most common observed risk is allergic transfusion reaction (ATR) that has an estimated frequency of <1% - 3% of all transfusions. **xxx,xxxii** Most ATR are mild and limited to urticarial rash, pruritis, flushing and/or fever. These are generally reversible events. Rare side effects include anaphylactic allergic reactions characterized by bronchospasm, angioedema and/or hypotension; and have an estimated frequency range from 1:591 to 1:2,184 plasma units transfused. Antibodies to human IgA that are passively transfused in the plasma into IgA deficient patients can cause dramatic anaphylactic reactions mediated by complement activation to small amounts of plasma containing IgA proteins. The prevalence ranges from 1:100 to 1:1000 in Caucasian, African American and Middle Eastern populations. **xxxii**

that the correct product was infused. Risk of infectious disease transmission is extremely low due to FDA required extensive donor medical screening and infectious disease testing. The estimated risk for acquiring HIV, HCV and HBV through transfusion is 1:1,467,000, 1:1,149,000 and 1:280,000 donations, respectively.

Hypothetical concerns regarding the use of convalescent plasma include the phenomenon of antibody-dependent enhancement of infection (ADE). For coronaviruses, several mechanisms for ADE have been described and there is the theoretical concern that antibodies to one type of coronavirus could enhance infection to another viral strain.xiv Because convalescent plasma will have titers of neutralizing antibody against COVID-19, ADE is not anticipated to develop. The anecdotal report of the use of convalescent sera in patients with SARS1 and MERS, and evidence from its use in 245 patients with COVID-19 acute infection suggest it is safe and has not resulted in ADE. Another hypothetical concern is that the use of convalescent plasma may suppress the hosts humoral immune response, thereby, leaving the patient vulnerable to subsequent reinfection. There is no data to substantiate this concern in prior use of convalescent plasma for coronavirus diseases. There is also the risk that convalescent plasma for COVID-19 infection may be ineffective.

The potential benefits of administering convalescent plasma have been outlined in Section 1.1. The infusion of convalescent plasma will likely provide immediate passive neutralizing antibodies against the virus. Historical observations for other viral pandemic infections have demonstrated lower risk for morbidity and mortality. Investigators have shown correlation of rapid reversal of inflammatory response to the infection and cytokines following infusion of convalescent plasma for the SARS Coronavirus. In the recent report from China, 245 patients were given convalescent plasma and it was concluded that approximately 35% showed clinical benefit. It is hoped that the administration of convalescent plasma to the study patients will reduce the severity and duration of the infection, and the risk for death.

2.0 Study Objectives

2.1 To transfuse COVID-19 infected patients with convalescent plasma and to observe whether this will result in a significant improvement in clinical outcome in comparison to historical experience. Patients eligible include the following study groups:

Group 3: As preemptive therapy for high-risk patients who present early with mild or non-severe COVID-19 infection.

- 1.1.2.1 **Primary objective** is whether this will reduce the probability of progressing to severe or critical disease significantly lower than the reported case rate (for Group 3 and 4, respectively).
- 1.1.2.2 Secondary objectives are to determine if this will impact the patient's clinical course including days in hospital, days on non-mechanical oxygen support, days with pneumonia and/or fever, days requiring ICU care, days on mechanical respirator/BIPAP, and death. Corollary laboratory studies will include days to viral clearance.

Group 4: As preemptive therapy for health care providers who have developed asymptomatic, mild or non-severe COVID-19 infection.

- 1.1.2.3 **Primary objective** is whether this will result in a lower risk of developing severe COVID-19 disease.
- 1.1.2.4 **Secondary objectives** are to determine if this will impact the patient's clinical course including days in hospital, days requiring ICU care, days on mechanical respirator/BIPAP, days on non-mechanical oxygen support, days with pneumonia and fever. Corollary laboratory studies will include days to

viral clearance.

3.0 Study Design

3.1 Overview of Study

COVID-19 infected patients will be screened per selection criteria shown in the Objectives and Study Population Sections. All patients must have confirmed COVID-19 disease and meet the inclusion and exclusion criteria established. Eligible patients for study after completing consenting process will be stratified into 4 treatment groups.

3.1.1 Primary and Secondary Endpoints and Efficacy Assessments

The primary endpoint of the study will be:

- 1) progression to severe disease for those with high-risk disease that present with mild/non-severe disease, and
- 2) progression to severe disease for health care workers who present with asymptomatic, mild or non-severe disease.

Secondary endpoints will include:

- 1) Acute care facility/hospital length of stay
- 2) Number of days requiring oxygen support
- 3) Number of days in an intensive care unit
- 4) Number of days on mechanical ventilation (invasive, noninvasive and ECMO)
- 5) Incidence of viral disease associated cardiomyopathy
- 6) Incidence of multi-organ dysfunction/failure
- 7) Safety of transfusion—Incidence of severe adverse events

3.1.2 Study Entry: Time from COVID-19 Infection Onset

3.1.2.1 High Risk group: Entry within 14 days of COVID-19 infection documentation.

Patients in the High-Risk group must present with either mild or non-severe disease for to be eligible for study entry; thereby, being identified early in the infection. These patients are to be entered and consented within 14 days of symptomatic COVID-19 infection documentation. Mild symptoms could include typical symptoms such as fever, dry cough, fatigue, nausea, emesis or diarrhea

3.1.2.2 Health Care Providers group: Healthcare worker must present with asymptomatic and with a positive NP swab; or mild or non-severe disease for to be eligible for study entry; thereby, being identified early in the infection. Asymptomatic patients must be enrolled within 14 days of the positive COVID-19 test. Mild or non-severe must be enrolled within 14 days of symptomatic infection documentation.

3.1.3 Additional Considerations for Study Design

- 3.1.3.3 Repeat testing for COVID-19 via nasal pharyngeal swab will be performed at 7 days and 14 days following infusion of convalescent plasma in all patients.
- 3.1.3.4 When available, serology testing for COVID-19 neutralizing antibodies will be measured prior to transfusion of convalescent plasma and again between 21 to 30 days following study entry (if test not available, sera sample(s) will be collected and stored).

3.1.3.5 Data for secondary objective endpoints will be collected and analyzed, including Charlson comorbidity index, KPS, and concurrent immunosuppressive therapy.

3.2 Number of Patients

The number of patients expected per each of the 2 groups:

Group 3: High Risk: n=159
Group 4: Health Care Providers: n=152

3.3 Duration of Study

Enrollment is expected to last for at least 48 months. This may be less or longer depending upon the pandemic outbreak patterns for recurrent flares infection peaking within the community. The study may be curtailed early if an effective vaccine is developed and there has been wide spread immunization.

3.4 Participant Duration

Participation in this study will last 30 days. For patients in the hospital longer than 30 days, the date of discharge will be noted regardless of the time.

4.0 Study Population

4.1 Inclusion Criteria for the selection of COVID-19 Infected Patients for Convalescent Plasma Transfusion

Each patient must meet all of the following inclusion criteria to be enrolled in the study:

- 1. Age ≥ 18 years
- 2. Documented COVID-19 infection with nasal pharyngeal sampling test by real time reverse transcription polymerase chain reaction (rRT-PCR), or nucleic acid amplification technology (NAAT) molecular testing. A partial list of available tests can be accessed at https://www.fda.gov/medical-devices/emergency-use-authorizations
- 3. Have COVID-19 Disease criteria that meets one of the 2 following groups:

4.1.1 Group 3: High Risk Patients with Mild or Non-severe Disease

- 1. Mild Disease: upper respiratory symptoms, cough, gastrointestinal symptoms (emesis, diarrhea, abdominal pain) or fever; but no radiograph evidence for viral pneumonitis.
- 2. Non-severe Disease: Chest radiographic changes compatible with COVID-19 disease, but no signs of respiratory compromise or hypoxemia.
- 3. High Risk condition must include one of the following: Immunocompromised (e.g. neutropenia, active chemotherapy for cancer or hematological malignancy, less than 12 months after undergoing allogeneic hematopoietic stem cell transplant or 100 days from autologous hematopoietic stem cell transplant, on systemic immunosuppressive therapy, history of solid organ transplant and poorly controlled HIV disease (e.g. CD4, 250/uL, recurrent opportunistic infections), insulin dependent diabetes mellitus, moderate to severe asthma history, severe COPD (DLCO < 60), morbid obesity (BMI ≥ 40),age ≥ 65 years, hypertension, moderate or severe cardiac disease (eg. Cardiomyopathy, CHF, moderate or

- severe valvular stenosis, ischemic heart disease), patients with severe renal disease (e.g. on dialysis), or liver disease
- 4. Informed consent signed within 14 days of symptoms developing for mild disease. For patients in the non-severe cohort, the time to consent must be within 14 days of positive chest x-ray or 14 days of first symptom whichever is longer (maximum 14 days to enrollment).

4.1.2 Group 4: Health Care Providers with asymptomatic, mild or non-severe disease

- 1. Health care providers who as part of their activities from time to time are at risk to exposure to COVID-19 infection. This includes administrative staff and ancillary support staff associated with hospitals or ambulatory clinic facilities.
- 2. Asymptomatic is defined as having diagnosis of COVID-19 without symptoms or clinical findings.
- 3. Mild or non-severe disease: Refer above for definitions.
- 4. Informed consent signed within 14 days positive COVID-19 test.

4.2 Exclusion Criteria for Selection of COVID-19 Patients

Patients meeting any of the following exclusion criteria are not to be enrolled in the study:

- 1. Known history of IgA Deficiency
- 2. History of anaphylactic reaction to blood product transfusion including hypersensitivity to immunoglobulin therapy.

5.0 Treatment Plan and Convalescent Plasma

5.1 Treatment plan for patients consented to receive convalescent COVID-19 donor plasma

5.1.1 Lab and Clinical Studies Pre-Transfusion (may be completed 72 hours before consent) (results are not required to be available prior to patient eligibility/administration of convalescent plasma but all tests must be completed before infusion)

- 1. Confirmation of COVID-19 positive nasal pharyngeal sampling test documentation of NP testing is required. Repeat testing is not required.
- 2. ABO Blood Typing and Cross & Match
- 3. CBC with platelets and differential
- 4. CMET including liver and renal function
- 5. COVID-19 neutralizing antibody titer (if test not available, to collect and store sera sample). Sample should be collected in an EDTA (lavender/purple or pink top tube)
- 6. Chest Radiographic study (CXR or CT-chest (preferred) within 72 hours of planned transfusion of Convalescent Plasma if clinically indicated.
- 7. Charlson Index Comorbidity Score (for all Groups)
- 8. Karnofsky Performance Score (for all Groups)
- 9. Baseline evaluation (see baseline treatment worksheet)
- 10. Recording of concurrent COVID-19 antiviral investigational therapy or other anti-viral therapies (e.g. IL-6 inhibitors (Tocilizumab), IL-1 inhibitors, hydroxychloroquine, ribavirin, lopinavir (for all Groups)
- 11. Recording of concurrent immunosuppressive medications (e.g. tacrolimus, cyclosporine, ruxolitinib, sirolimus, prednisone (steroids), Rituximab (within prior 12 months), chemotherapy treatment in prior 6 months, rheumatology therapy, Crohn's Disease or Ulcerative Colitis therapy) (for all Groups).
- 12. Documentation of days of symptoms preceding infusion of convalescent plasma (fever, cough, shortness of breath/dyspnea, emesis, diarrhea, abdominal pain, pharyngitis) (for all Groups)

5.1.2 Transfusion of COVID-19 Convalescent Plasma

1. Following verification of study eligibility and consenting of the subject, the Atlanta

Blood Center (or blood center providing the plasma) and the hospital blood bank will be notified to assign and release a Convalescent Donor Plasma Product. The intent is to release the product for transfusion within 24 hours following the consent being signed. On occasion a delay beyond 24 hours may occur if there is a scheduling delay for a courier to transport the product to an outlying hospital facility, or there is a delay due to waiting for a donor plasma product to complete release criteria as established by the FDA.

- Directed Donor Convalescent Plasma Product(s) to have a two-person verification per institution protocol for identification of patient and product prior to transfusion of product(s).
- 3. Convalescent Plasma Product to be provided in 200-425 ml transfusion pack. The bag will be transfused (over at least 2 hours).
- 4. If patient demonstrates non-severe allergic transfusion reaction or any other mild adverse reaction to the plasma infusion, the infusion is to be held until resolution of signs and symptoms. Following evaluation and assessment by medical team that may include need for antihistamine, corticosteroid and/or diuretics administration, transfusion may be restarted at a slower infusion rate per directive of medical team.
- 5. If patient develops anaphylactic reaction or severe acute reaction, then the transfusion should be stopped. Institutional policy for managing severe transfusion reactions should be initiated in consultation with medical team.

5.1.3 Laboratory and Clinical Monitoring Post-COVID-19 Convalescent Plasma Infusion

- 5.1.3.1 Fever (maximum value) monitoring daily through D30. For patients who are discharged from the hospital, they will be provided the diary and asked to complete it from discharge until Day 30.
- 5.1.3.2 For patients in group 3 and 4, they will be asked to maintain a daily diary log for symptoms through day +30
- 5.1.3.3 Recording of inpatient hospital days, days in ICU, days on mechanical ventilator (invasive and noninvasive).
- 5.1.3.4 Chest radiograph (CT chest or CXR) on days 7 and 14: for patients in groups 3 and 4, if a baseline chest xray/radiograph was completed, follow up radiographic studies will be required on days 7 and 14.
- 5.1.3.5 COVID-19 sera neutralizing antibody titer (when test is available) to be obtained between days 21-30 following infusion of convalescent plasma. If test is not available sera will be collected and stored. This will be collected in an EDTA tube (lavender/purple or pink top)
- 5.1.3.6 COVID-19 NP swabs will be repeated all subjects on Days 7 & 14.

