Use of Convalescent Plasma Collected From Donors Recovered From COVID-19 Virus
Disease for Transfusion, as an Empirical and Preemptive Treatment during Viral
Pandemic Outbreak

Principal Investigator: [name]

Protocol version: 12/7/2020

Protocol Summary

Study Title: Use of Convalescent Plasma Transfusion, Collected From Donors Recovered From COVID-19 Virus Disease, as an Empirical and Preemptive Treatment during Pandemic Outbreak

Phase II

Expected Numbers of Patients:

Group 3: High risk patients n=159
Group 4: Health Care Providers n=152

Study Objectives:

- 1. To transfuse COVID-19 infected patients with convalescent plasma and to observe whether this will result in a significant improvement in clinical outcome in comparison to historical experience. Patients eligible include the following study groups:
- **Group 3:** As preemptive therapy for High Risk Patients who present with mild or non-severe COVID-19 infection.
- **Group 4:** As preemptive therapy for health care providers who have developed asymptomatic, mild or non-severe COVID-19 infection.
- **a. Primary objective** is whether infusion of convalescent plasma will reduce the probability of progressing to severe or critical disease significantly lower than the reported case rate (for Group 3 and 4, respectively).
- **b. Secondary objectives** are to determine if infusion of convalescent plasma will impact the patient's clinical course including days in hospital, days requiring ICU care, days on mechanical respirator/BIPAP, days on non-mechanical oxygen support, days with pneumonia, fever, and viral clearance.

Overview of Study Design

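### Swabs on Days 7 and 14, and films in only part of the cohort, cannot give days to viral clearance or days with pneumonia; report Day 7 and Day 14 proportions instead

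*Combined protocol and SAP*

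**What the plan says.** **Objectives.** The Protocol Summary lists "days with pneumonia, fever, and viral clearance" among the secondary objectives. Section 2.0 lists "days on non-mechanical oxygen support, days with pneumonia and/or fever" for Group 3 and similar items for Group 4. For both groups it adds "Corollary laboratory studies will include days to viral clearance".

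**Swabs.** Section 5.1.3 states "COVID-19 NP swabs will be repeated all subjects on Days 7 & 14". Section 3.1.3 gives the same times: repeat testing "will be performed at 7 days and 14 days following infusion of convalescent plasma in all patients". No later swab is scheduled, although participation runs to 30 days (section 3.4). Before transfusion, section 5.1.1 asks for documentation of the earlier positive test and adds "Repeat testing is not required". Section 4.1.2 lets Group 4 consent up to 14 days after that test.

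**Films.** Section 5.1.1 asks for a chest film or CT in the 72 hours before transfusion only where there is a clinical reason. Section 5.1.3 then says that, "if a baseline chest xray/radiograph was completed, follow up radiographic studies will be required on days 7 and 14". The severity definitions make pneumonia a radiographic finding.

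**Analysis.** Section 6.2.1 compares secondary endpoints with historical or matched controls. It names neither measure and gives no method for interval-censored times. The secondary endpoint list in section 3.1.1 does not contain them either.

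**The concern.** A duration in days needs a known start and an end observed closely enough to date it. Here the virus is looked for twice after infusion, a week apart, and not necessarily at time zero. Infiltrates are looked for on the same two days, and only in some patients. The plan defines neither clearance nor the end of pneumonia, so the analyst would have to choose a dating rule once the data are in, in a study without concurrent controls.

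Three things are at stake:

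- If historical controls were swabbed or filmed on another schedule, a difference in days would partly measure the schedules.
- Clearance before infusion could be read as clearance after plasma.
- Pneumonia that starts in a patient without a baseline film has no scheduled film to find it.

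**Working it through.** The plan gives no figure for these measures, so there is none to reproduce. The check sets the schedule against the objectives and sizes two consequences.

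**1. What the swabs can show.** With swabs at Days 7 and 14, a patient is negative by Day 7, first negative between Days 7 and 14, or still positive at Day 14. The COVID-19 plasma series cited in the background reports clearance in seven of seven patients at a median of 3 days, range 2 to 6. On this schedule all seven would fall in the first class, with nothing to separate day 2 from day 6.

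**2. Size of the dating error if the first negative swab were taken as the clearance date.** The plan does not state this rule; it is the simplest one an analyst might adopt. Assume exponential clearance after infusion with a median of 7 days.

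- Mean time = 7 / ln 2 = 7 / 0.693 = 10.10 days.
- Mean time among those cleared by Day 7 = 10.10 − 7 × 0.5 / 0.5 = 3.10 days.
- Average delay = 7 − 3.10 = 3.90 days. It is the same in the second week because the exponential has no memory.
- Still positive at Day 14 = 0.5^(14/7) = 25%.

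Simulation over assumed medians of 3 to 14 days (exponential, and lognormal with log-SD 0.5) gives an average delay of 3.0 to 4.4 days among those cleared by Day 14, with 0% to 50% still positive then. With true medians of 3 or 5 days, 62% to 95% are negative at the first swab. Both medians would be recorded as Day 7, and a two-day difference would not show.

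**3. Status at infusion.** For a Group 4 patient who is negative on Day 7, the last known positive may be 14 + 7 = 21 days earlier, plus any delay between consent and infusion. Clearance may have come before infusion.

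Let f be the share already negative at infusion, and q the share of the others who clear by Day 7. If those already negative stay negative:

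- Observed Day 7 proportion = f + (1 − f)q.
- Inflation = f + (1 − f)q − q = f(1 − q).

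The documents give neither f nor q, so both are assumptions. Observed proportion, with the inflation in points in brackets:

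| f | q = 30% | q = 50% | q = 70% |
|---|---|---|---|
| 10% | 37% (7) | 55% (5) | 73% (3) |
| 20% | 44% (14) | 60% (10) | 76% (6) |
| 30% | 51% (21) | 65% (15) | 79% (9) |

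**4. What the films can show.** A patient without a baseline film has no scheduled film. A patient with one has three scheduled points (baseline, Day 7, Day 14), so resolution falls before Day 7, between Days 7 and 14, or after Day 14 and unseen. Section 5.1.3 has fever and symptoms followed daily to Day 30. Fever days can therefore be counted, but the diary records neither virus nor infiltrates.

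**5. Reach.** Section 6.1 sizes the trial on progression proportions (25% against 16.3%, and 14.8% against 7.5%). Neither measure enters that calculation.

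**The case against.** The strongest reply is that these are minor measures. Section 2.0 calls viral clearance corollary, section 3.1.1 lists neither measure, and no dating rule is stated that could be called wrong. A documented positive swab is mandatory for every patient. Patients entered as non-severe must have had a radiographic finding, so the filmed subset should hold most of those with pneumonia at entry. And if clearance is as fast as in the cited series, q is near 1 and the inflation near zero.

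Much of this stands, and it limits the point:

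- A reader might infer that there is no baseline swab. There is one; what is missing is a swab at infusion.
- The 14-day age of the test is stated for Group 4. For Group 3, section 4.1.1 counts from symptoms or chest film, and section 3.1.2.1 from documentation of symptomatic infection.
- A reader might infer that a share f already negative inflates the Day 7 result by f. That holds only if q = 0.
- The cited series was in severe patients, so it is only indicative for q here.
- The film that made a patient non-severe may predate the 72-hour window, and the plan does not say whether it counts as the baseline film. The clear gaps are unfilmed patients who develop pneumonia later and resolution after Day 14.

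The reply does not rescue the durations. The objectives ask for days, and the schedule does not collect them.

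**Conclusion.** The point holds for durations. As scheduled, the trial cannot report days to viral clearance or days with pneumonia in any form that is not largely set by the visit days. That follows from the schedule alone and rests on no assumption.

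The sizes do rest on assumptions. The Day 7 inflation is f(1 − q): 5 to 15 points at q = 50% with f = 10% to 30%, and 3 to 21 points over the wider grid. The dating delay of 3.0 to 4.4 days depends on the assumed clearance curves and on a rule that the plan does not state.

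Two stronger readings are not supported. One is that the trial says nothing about clearance: the swabs do give the proportion negative on each day, or an interval-censored estimate. The other is that the main result is compromised: the primary endpoint, sample size, interim rule and listed secondary endpoints do not use these measures. The change should be made, but it concerns secondary or corollary objectives only.

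**What to change.** **Virus.** In the Protocol Summary and section 2.0, replace the clearance duration with the proportion swab-negative at Day 7 and at Day 14, each with a score interval (the type section 6.3 already uses). Call it swab-negative, not cleared because of plasma: the proportions remove the false precision but not the unknown status at infusion. Reporting each day separately also avoids needing a rule for a patient negative on Day 7 and positive on Day 14.

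**If a time is wanted.** Use an interval-censored estimate with bounds set for each patient, from the date of the last documented positive swab to the date of the first negative one, right-censored at Day 14 if still positive. State the time origin. Fixed bounds of 0–7, 7–14 and over 14 days run from infusion and do not fit a clock started at the qualifying test. Counted from that test, a Group 4 patient infused 14 days later and negative on Day 7 has the interval 0 to 21 days.

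**Pneumonia.** Replace the duration with the proportion with infiltrates at Day 7 and at Day 14 among patients with a baseline film. State that denominator and which film counts as baseline. Days with fever can stay, as a separate item.

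**Consistency.** Bring the endpoint list in section 3.1.1 and the analysis in section 6.2 into line, since neither names these measures now.

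**Cost.** Wording only, with no extra tests. The endpoints are described less finely, but no information that the schedule collects is lost. Crediting clearance to the period after infusion would need a swab on the day of infusion, which is an added test and not part of this change.
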